### *2. Clinical trial title*

"Treatment of proximal humeral fractures with sling." Prospective, non-randomized and open study to evaluate the effectiveness of orthopedic treatment in the management of three and four-parts proximal humeral fractures according to Neer's classification.

### *5. Ethical Committee for Clinical Research evaluating the trial*

CEIC of Gregorio Marañón University Hospital

### *6. Objectives:*

#### 1. Main:

Evaluate the effectiveness of conservative treatment in the management of fractures in 3 and 4 fragments of the proximal humerus according to Neer classification, in patients over 75 years of age.

#### 2. Secondary:

- Compare the results obtained with a historical surgical cohort that were treated with shoulder arthroplasty for this same pathology.
- Evaluate possible complications from orthopedic treatment.

### *7. Design*

Unicentric, prospective, non-randomized, open clinical trial comparing the effectiveness of the orthopaedic treatment for three and four-parts proximal humeral fractures in a patient population over 75 years of age.

Two treatments for these fractures will be compared secondarily:

1. Shoulder arthroplasty
2. Conservative treatment with sling followed by physiotherapy.

Both options are accepted today for the management in this type of fractures. [1, 2]

### *8. Valuation variables:*

1. Main:

Efficiency measured by the use of 4 valuation scales:

a. ***THE AMERICAN SHOULDER AND ELBOW SURGEONS EVALUATION SCALE (ASES)***

*J Shoulder Elbow Surg* 1994;3:347-352.

It includes subjective information on the part of the patient and the result of a physical examination. It is possible to get a score with a maximum of 100 points, of which 50% obtain them from the subjective perception of pain and the activities of daily life.

b. ***DASHe ( Disability of Arm. Shoulder and Hand)***

*Spanish version of the DASH quartet. Med Clin ( Barc).2006;127(12):441-7*

without valuing the professional and work module.

For the final score, at least 27 of the 30 questions need to be answered. The final score is obtained by calculating the arithmetic mean of the answered questions, subtracting 1 and multiplying by 25. This calculation provides a score between 0 and 100, with the greater the disability at the highest point obtained, and considering variations with clinical significance those exceeding 10 points.

$$\left( \frac{\text{Sum of n answers}}{n} \right) - 1 \times 25$$

c. **Constant Scale**, *Clin. Orthop. Relate. Res 1987:160-4.*

It is the most used questionnaire for shoulder evaluation. It includes a subjective assessment of the pain presented by the patient, up to 15 points, the ability to perform daily activities, up to a maximum of 20 points, objective mobility assessment, up to 40 points, and strength through physical examination, up to 25. The maximum score is 100., considering results as excellent > 80, good 65-79, media 50-64, and bad <50.

d. **VAS (analog visual scale)** *Thong ISK, Jensen MP, Miró J, Tan G. The validity of pain intensity measures: what do the NRS, VAS, VRS, and FPS-R measure? Scand J Pain. 2018 Jan 26;18(1):99-107.*

It is defined as a one-dimensional scale for subjective assessment of pain by the patient. It consists of a straight line (usually 10 centimeters -100 millimeters-) at whose limits are the most extreme degrees of pain intensity, considering a score of 0 points for the lowest degree or absence of pain (usually referred to by the

patient as "painless") and 100 points for the highest degree (usually referred to as "the worst bearable" or "worst pain imaginable").

The final score (between 0 and 100 points) is obtained by measuring the distance in millimeters between the lower end (0-point score) and the mark the patient points along the line.

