## 9. Hypothesis

NULL hypothesis : The use of **non-surgical** treatment for three and four-parts proximal humeral fractures in elderly people (over 75 years) does not produce a statistically significant functional improvement.

MAIN hypothesis : The use of **non-surgical** treatment for three and four-parts proximal humeral fractures in elderly people (over 75 years) produces a statistically significant functional improvement.

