## **OBJECTIVES**

1. Main:

Compare the effectiveness of conservative treatment for the management of three and four-parts proximal humeral fractures in patients over 75 years of age.

2. Secondary:

- Compare the results obtained with a historical surgical cohort treated with shoulder prostheses for this same pathology.
- Evaluate possible complications from orthopedic treatment.

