## Statistical analysis

1 Sample size: Accepting an alpha risk of 5% and a beta risk of 20% in a bilateral contrast, 20 patients are required in each group to detect a difference equal to or greater than 13 units in the ASES scale score. The common standard deviation is assumed to be 15.

2 Statistical analysis: Qualitative variables shall be expressed as absolute frequencies and percentages while quantitative variables shall be presented as typical means and deviations or as medians and inter-quarterlic range depending on their normality.

Initially, the comparability of both groups will be studied to check the homogeneity of the randomization groups. Comparisons of the ASES scale and all other numeric variables between two groups will be made with student's t-test of independent measurements or Mann-Whitney test, as deemed appropriate. For repeated measurements at 3 and 12 months, the Student's t of repeated measurements or Wilcoxon test shall be used. To study the association of categorical variables, the Pearson ji-square or Fisher exact test will be used.

Differences whose p-value associated with the contrast test is less than or equal to 0.05 shall be considered significant. Data collection will be recorded in Excel database which will then be exported and analyzed in the SPSS 18 statistical program.

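### Four unranked scales are all main variables for one hypothesis, with no hierarchy, adjustment or any/all rule, while the sample size allows 5% alpha for a single ASES contrast

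*Combined protocol and SAP*

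**What the plan says.** **Main variables.** Section 8 (Valuation variables, Main) gives the main variable as "Efficiency measured by the use of 4 valuation scales" and lists ASES, DASH, Constant and VAS as items a to d, without ranking. All four are recorded at 3 and 12 months (Follow-up period, Shoulder consultation).

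**Hypothesis.** Section 9 has one null and one main hypothesis. The main one is that non-surgical treatment "produces a statistically significant functional improvement". It names no scale, visit or contrast.

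**Objective.** Section 6 reads "Evaluate the effectiveness of conservative treatment in the management of fractures in 3 and 4 fragments of the proximal humerus", which concerns the conservative group alone. The later OBJECTIVES section reads "Compare the effectiveness of conservative treatment for the management of three and four-parts proximal humeral fractures", without saying against what.

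**Two-group comparison.** Sections 6, 7 and 8 all class the comparison with the historical arthroplasty cohort as secondary, and section 8 names only the Constant scale for it.

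**Analysis.** The Statistical analysis section plans both types of test: "Comparisons of the ASES scale and all other numeric variables between two groups will be made with student's t-test" (or Mann-Whitney), and "For repeated measurements at 3 and 12 months, the Student's t of repeated measurements or Wilcoxon test shall be used". Its decision rule is "Differences whose p-value associated with the contrast test is less than or equal to 0.05 shall be considered significant".

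**Sample size.** The same section states that "20 patients are required in each group to detect a difference equal to or greater than 13 units in the ASES scale score", with a two-sided 5% alpha, 80% power and a common SD of 15.

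No section gives a hierarchy, a multiplicity adjustment, a composite, or a rule on whether one scale or all of them must reach significance.

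**The concern.** One hypothesis is to be judged on four scales, and the plan does not say how four p-values become one conclusion. If a single significant scale counts as support, the error rate for the main claim exceeds the 5% used in the sample size. If all four must be significant, the error rate is controlled, but the power of the joint requirement is below that of each single test. If the scales disagree, for example pain improves and function does not, nothing in the plan resolves it.

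The contrast is open as well. A paired 3 versus 12 month test in the conservative group is one plausible reading of section 6 and the visit schedule. A between-group test is another, because that is what the sample size addresses. With scale and contrast both unfixed, the rule for success can be chosen after the results are known.

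**Working it through.** **Inputs from the documents.** Four main scales (section 8); 20 conservative and 20 historical patients (section 10); two-sided alpha 0.05, power 80%, ASES difference 13, SD 15 (Statistical analysis).

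**Assumed inputs.** The documents give no correlation between scales or between visits. A common between-scale correlation of 0, 0.5, 0.8 and 0.95 is used, and a between-visit correlation of 0.3, 0.5 and 0.7.

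**1. The plan's own figure.** The normal formula gives n per group = 2 × [15 × (1.960 + 0.842) / 13]² = 20.9, so 21 against the stated 20. Exact t-test power with 20 per group is 76.1%; 80% needs 22 per group. The stated figure is close, but it covers one ASES contrast at the full 5%, with no allowance for three further main scales.

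**2. Any one of four suffices, no true effect.** For independent scales the error is 1 − 0.95⁴ = 18.5%. For correlated scales it was simulated with t-tests:

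| Correlation between scales | Paired, n = 20 | Two-group, 20 vs 20 | Paired, favourable direction only |
|---|---|---|---|
| 0 | 18.6% | 18.7% | 9.7% |
| 0.5 | 15.9% | 15.7% | 8.0% |
| 0.8 | 11.7% | 11.5% | 5.8% |
| 0.95 | 8.2% | 8.1% | 4.1% |

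A single test has 5% two-sided and 2.5% in the favourable direction. The inflation hardly depends on which contrast is meant.

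**3. All four must succeed.** The false-positive rate is at most 5%. In simulation it reached 5% when three scales had a large true effect and one had none. The cost is joint power:

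| Setting (same effect on every scale) | Single-test power | Joint power, correlation 0 / 0.5 / 0.8 / 0.95 |
|---|---|---|
| Each test at exactly 80% | 80% | 41 / 55 / 65 / 73% |
| Two-group, 13 units, SD 15 | 76.1% | 34 / 49 / 60 / 69% |
| Paired, 13 points, SD 15, visit correlation 0.3 | 87.4% | 58 / 69 / 76 / 82% |
| Paired, visit correlation 0.5 | 95.7% | 84 / 87 / 91 / 93% |
| Paired, visit correlation 0.7 | 99.7% | 99% throughout |

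The paired rows borrow 13 and 15 from the two-group calculation, because the documents give no effect or SD for within-group change.

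**4. What 20 patients can detect on one paired ASES contrast.** A paired t-test with n = 20 has 80% power at a standardized change of 0.660. The detectable change is 0.660 × 15 × √[2(1 − r)], which is 11.7, 9.9 and 7.7 points for r = 0.3, 0.5 and 0.7.

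**5. Two-group alternatives.** For 13 units and SD 15, power is 80.2% with 22 vs 22 and 80.6% with 25 vs 20. With 20 vs 20, the difference detectable with 80% power is 13.6 units.

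**The case against.** The strongest reply is that ASES is already the lead scale in practice: it is listed first, it is the only scale sized, and it is the only one named in the between-group test sentence. That is a fair hint, but no section declares it primary. The sized ASES contrast belongs to a comparison classed as secondary, and section 8 names Constant, not ASES, for that comparison.

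Second, the larger percentages may overstate the problem. The hypothesis claims improvement, so only favourable results could support it. ASES and Constant both include pain and daily activities, and VAS is pain, so near-independence is unlikely. VAS might also not count as function at all, leaving three scales. All of this stands as a matter of size. With three scales the any-one error is still 14.3% if independent (1 − 0.95³) and about 7.5% at correlation 0.95. In the favourable direction, four scales give 4% to 10% against 2.5%. In the other direction, 18.5% bounds only four tests of one contrast; eight independent tests (four scales at two visits) would give 1 − 0.95⁸ = 33.7%.

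Third, if the main contrast is the uncontrolled change from 3 to 12 months, the missing comparator is the larger threat to interpretation, and naming one scale does not cure it. That is true and should be stated in the plan.

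Finally, this is a small, single-centre, open study. That limits the severity. But the plan states a hypothesis, an alpha, a power and a significance threshold, so it needs a rule for applying them.

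**Conclusion.** The concern holds. The main hypothesis has four unranked main variables, no fixed visit or contrast, and a blanket 0.05 threshold, while the 5% alpha was budgeted for one ASES contrast.

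Inflation arises only under an any-one rule, and its size rests on assumed between-scale correlations, with the lower part of the range more realistic. Under an all-four rule the error rate is controlled; joint power below 80% is possible but not certain, because the effect and SD for within-group change are not given. The gap between 76% and 80% power is a side point.

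The correction should be made but is not critical. It is more than missing detail, because the stated rule lets the main claim exceed its 5% error or rest on a choice made after the results are seen.

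**What to change.** Name one primary scale, one visit and one contrast in sections 6, 8 and 9, the OBJECTIVES section and the Statistical analysis section, and limit the confirmatory 0.05 rule to that test. ASES is the natural candidate because it is the only scale sized. Two versions are possible:

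- **(a) Conservative group alone.** Primary: within-group ASES change from 3 to 12 months, paired test. Restate the sample-size sentence for this contrast. With SD 15 at each visit, 20 patients detect 11.7, 9.9 or 7.7 points at an assumed between-visit correlation of 0.3, 0.5 or 0.7, so no extra patients are needed. State that the contrast is uncontrolled, that its starting point comes after the sling phase, and that it shows recovery between 3 and 12 months which cannot be attributed to the treatment.
- **(b) Two-group difference.** Primary: ASES at 12 months between groups. Reconcile the secondary status in sections 6, 7 and 8 and the restriction to Constant in section 8. State power of about 76% for 13 units with 20 per group, or a detectable difference of 13.6 units. To keep 13 units at 80% power, plan 22 per group, or 25 conservative patients if the historical cohort stays at 20. The comparison remains non-randomized and historical. Confirm first that ASES was recorded in that cohort, which the documents do not say.

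In either version, make DASH, Constant, VAS and the other visit-specific contrasts secondary, reported as estimates with 95% confidence intervals or Holm-adjusted. The cost is wording and a restated sample-size sentence, plus extra patients only if (b) is kept at 13 units with 80% power. Three scales lose primary status.

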## 2. Secondary:

- Comparison of the results obtained on the Constant scale with a surgical historical cohort that were treated by shoulder prostheses for this same pathology.
- Complications arising from non-surgical treatment.

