## **BACKGROUND AND CURRENT STATE.**

Proximal limb fractures of the humerus are very common, representing 10% of all fractures, with an incidence of 6.6/1,000 people and year, with exponential increase from 40 years. [3-6]

Most of these fractures do not have displacement so they are successfully treated with brace immobilization and subsequent rehabilitation.

Fractures with displacement of the fragments require surgical management. We classify these fractures according to the number of fragments displaced in 1, 2, 3 and 4, according to the system proposed by Neer.

Displaced fractures type 3 and 4 of the Neer classification affecting older patients have been the subject of numerous studies with the aim of establishing the most appropriate treatment. [7,, 8]

Reconstruction with shoulder replacement, both inverted and anatomical, has been widely used as a treatment in these fractures; different studies have been launched to establish which of the two prosthetic models offers the best [1,, 9-13]. [14,, 15]

In older patients, where functional demand is not as demanding and where shoulder arthroplasty may cause various, conservative management can get a good clinical outcome in displaced fractures affecting the humeral neck. (17) [2, 15, 16]

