## **JUSTIFICATION OF THE STUDY**

We know the result of surgical treatment for three and four-parts proximal humeral fractures in older patients, but it was to be established if these are superior to the results obtained with conservative treatment.

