## **TYPE OF TEST AND DESIGN**

### **Selection process:**

Patients candidates for conservative treatment (three-week sling) will form the "cases" group and will be selected by the research team after their emergency care. They will be informed of the existence of this study and offered to participate in it; if they become part of the study, patients will receive orthopedic (non-surgical) treatment of their humeral fracture. Informed consent will then be given to the patient.

The "control" group will be formed by patients undergoing surgical treatment who will be selected from a historical cohort from a previous clinical trial. (FRALUX)

Patients who decline to be part of the study will receive the same treatment currently offered in our Traumatology Service, being able to manage their fracture either through surgical techniques (shoulder prostheses) or through immobilization and subsequent rehabilitation treatment. Assigning one treatment or another to each patient will depend on multiple clinical, radiological variables and the patient's own decision as has been made at the current time in our clinical practice.

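### Complications are specified only for the sling group, so the secondary comparison with arthroplasty holds no surgical complications or re-operations and cannot support a conclusion about overall superiority

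*Combined protocol and SAP*

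**What the plan says.** - **Harms outcome.** Section 8 (Valuation variables, Secondary) lists "Complications arising from non-surgical treatment". The matching objective in section 6, repeated under OBJECTIVES in the body, is "Evaluate possible complications from orthopedic treatment". The Selection process section shows that orthopedic here means non-surgical: "patients will receive orthopedic (non-surgical) treatment of their humeral fracture".
- **Comparison with surgery.** Section 7 (Design) says that the two treatments will be compared as a secondary matter. Section 8 gives that comparison one named outcome: "Comparison of the results obtained on the Constant scale with a surgical historical cohort". The Statistical analysis section is wider and plans "Comparisons of the ASES scale and all other numeric variables between two groups".
- **Question behind the comparison.** JUSTIFICATION OF THE STUDY takes the surgical results as known and says that "it was to be established if these are superior to the results obtained with conservative treatment".
- **Data collection.** The shoulder visits are at 3 weeks, 3 months and 12 months. The last two list the four scales. None lists a complication item.
- **Source of the surgical group.** Selection process and Treatment description say that these patients come from a previous clinical trial and were evaluated there. Section 10 puts their number at 20.

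**The concern.** Whether one treatment is superior overall depends on its complications and re-operations as well as on its scores. The plan sets up a comparison of two treatments but makes complications an outcome for only one of them. A Constant or ASES difference in favour of arthroplasty could then be read as overall superiority with no surgical harms set against it. A difference in favour of the sling, or no difference, would be equally incomplete. At stake is what the secondary comparison can conclude. The main single-group question about the sling is not affected.

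**Working it through.** The point rests on the text. Arithmetic comes in only to show what a two-group complication outcome could deliver.

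**1. The passages side by side**

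| Item | Sling group | Historical arthroplasty group |
|---|---|---|
| Complications objective (section 6; OBJECTIVES) | Yes | Not mentioned |
| Complications variable (section 8) | Yes | Not mentioned |
| Constant score (section 8) | Yes | Compared |
| ASES and other numeric variables (Statistical analysis) | Yes | Compared |
| Re-operation or later shoulder surgery | Not mentioned | Not mentioned |

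Two places might be thought to fill the gap. The comparative objective in section 6 and under OBJECTIVES speaks broadly of results, but section 8 turns it into the Constant scale. The Statistical analysis section names chi-square and Fisher tests for categorical variables, but it names no variable, and a test cannot analyse surgical events that no section defines or collects.

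**2. The plan's own sample size**

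Inputs (Statistical analysis): ASES difference 13, SD 15, two-sided alpha 5%, power 80%.

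n per group = 2 × [15 × (1.960 + 0.842) / 13]² = 20.90, rounded up to 21. The noncentral t calculation gives 22. At 20 per group, power is 78.3% (normal) or 76.1% (t). The stated 20 is reproduced closely and is not in dispute. It was set on ASES, not on complications.

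**3. What 20 per group gives for complications**

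The documents give no complication rates, so every count and rate below is an assumption.

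- Exact (Clopper-Pearson) 95% interval for 0/20: the upper limit is 1 − 0.025^(1/20) = 16.8%, so 0% to 16.8%. For 4/20 it is 5.7% to 43.7%.
- Two-sided Fisher, 0/20 versus 4/20: p = 2 × C(20,4)/C(40,4) = 2 × 4,845/91,390 = 0.106.
- Two-sided Fisher, 0/20 versus 5/20: p = 2 × C(20,5)/C(40,5) = 2 × 15,504/658,008 = 0.047. With no events in one group, this is the smallest contrast that reaches 0.05.
- Exact power of Fisher's test at two-sided 5%, 20 versus 20:

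| Assumed rates | Power |
|---|---|
| 5% vs 15% | 7% |
| 5% vs 20% | 17% |
| 10% vs 30% | 24% |
| 5% vs 30% | 45% |
| 5% vs 40% | 72% |

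Only a very large difference would be detected reliably. Counts with intervals would still be informative, but they could not exclude a sizeable difference.

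**The case against.** The strongest reply is that this is essentially a single-group study. The title, main objective and hypotheses concern the sling alone, and the surgical comparison is secondary. Listing the complications of the treatment under study is coherent with that. The surgical patients were already evaluated in an earlier trial, so their complications may be on record and could be cited. Much of this stands: it limits the weight of the point, and the documents do not show what the investigators hold. It does not close the gap, because the comparison is a stated objective with planned between-group tests, and no section brings surgical harms into it.

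A reader might infer more than the documents support:

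- **That surgery is compared on function alone.** Section 8 gives up to 15 of the 100 Constant points to pain, ASES also covers pain, and the Statistical analysis wording would take in the VAS.
- **That the plan expects the sling to win on complications.** The background says "where shoulder arthroplasty may cause various, conservative management can get a good clinical outcome in displaced fractures", but the noun after the word various is missing from the text. It hints at a drawback of arthroplasty. No section predicts a lower complication rate with the sling.
- **That the report would show surgery as free of complications.** No table of that kind is prescribed, and an outcome that is not collected is not a count of zero.
- **That the wording builds in biased attribution of events.** The phrase in section 8 stands in an apparently translated text, the objectives use looser wording, and no attribution procedure is described.
- **That existing data would be discarded.** The documents do not say whether the previous trial recorded these events, or for how long.

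**Conclusion.** The point holds as a gap in a secondary comparison that should be corrected. Complications are an outcome for the sling group only, and the arthroplasty cohort enters on functional and pain scores. A statement that either treatment is superior overall would therefore go beyond what the plan collects.

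Its size cannot be put as a rate, because the documents give none. Under the assumed rates from 5% versus 15% up to 5% versus 30%, power is about 7% to 45%, so the remedy gives a descriptive result with wide intervals and not a test. The conclusion rests on reading orthopedic as non-surgical, which the Selection process section states, and on the absence of any section that provides for surgical complications. It does not touch the main objective or the stated sample size.

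**What to change.** 1. In section 6, section 8 and OBJECTIVES, replace the sling-only item with one outcome for both groups: shoulder-related complications and any subsequent shoulder surgery or re-operation within 12 months, from one common list. State that the initial arthroplasty is the treatment received and does not count as an event.
2. For the sling group, record these events at the existing 3-week, 3-month and 12-month visits. For the 20 surgical patients, extract them from the previous trial's records.
3. In Statistical analysis, add that counts per group and the risk difference with an exact 95% interval will be reported beside the score comparison, descriptively. State that retrospective capture in the surgical group may be less complete than prospective capture.
4. Add a fallback: if the earlier records do not hold these events, say so and limit the comparative conclusion to functional and pain scores.

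The cost is a short amendment, one extra item on the data collection sheet at visits already planned, and a record extraction for 20 patients. No extra patients or visits are needed. The downside is unequal completeness between the groups, which has to be declared.
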